**IPSS questionnaire**

Scores with at least 1 but not more than 50% missing items will be imputed using the formula:  $S = s \times T \div t$  where s is the observed score, S is the imputed score, T is the maximum total score for the IPSS and t is the maximum score possible from the completed questions. Missing total scores will be imputed using a multiple imputation method (Markov Chain Monte Carlo method).

Other missing data, including biopsy data, will not be replaced.

A subject with missing Month 12 biopsy will be counted as failure for the primary analysis.

**Statistical plan and methods**

All analysis will be carried out using contemporary versions of Stata or R.

The data collected in this study will be listed for each subject and summarized as appropriate for each treatment group as described below.

Continuous variables will be described using: number of available observations, median, first quartile (Q1), third quartile (Q3) using three significant figures.

Qualitative variables will be summarized by number of observations and percentages (%). Percentages will be rounded to two significant figures and will be based on available observations, unless otherwise specified.

***Background characteristics*****Subject disposition**

The overall number of screen failures will be presented.

The number of subjects consented, who completed the study, who discontinued early and the reasons for early terminations will be summarized by treatment group.

The number of subjects receiving retreatment at 3 months will be presented.

**Demographic and baseline characteristics**

Demographic characteristics such as age, gender, ethnic origin, height, weight and BMI will be summarized. Specific baseline disease characteristics such as time since diagnosis, TNM staging, PSA, prostate volume, type of disease (unilateral/bilateral), total number of positive cores will be summarized.

**Treatment modalities**

The number of fibres used, the energy applied and the light density index will be summarized for the VTP treatment group using standard descriptive statistics.

***Efficacy analysis***

All analyses will include the “efficacy population” as described above with a secondary analysis including patients undergoing retreatment at 3 months.

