6.4.10 Additional Visits

A single re-treatment of lobes found positive for cancer at 3-months follow-up is allowed.

Those additional treatments will be performed in the same conditions as for the first VTP procedure (section 6.4.2.). The schedule of visits will remain unchanged and the whole study duration will be sixty months.

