10.3 Analysis of primary endpoint

The primary efficacy variable is the result of the Month 12 biopsy, in which success is defined by absence of detectable Gleason grade 4 or 5 prostate cancer in any given biopsy.

The primary endpoint will be analysed as a dichotomous outcome, i.e., success (absence of any histology result positive for Gleason 4 or 5 prostate cancer at 12 months) or failure (presence of at least one result positive for Gleason grade 4 or 5 prostate cancer at 12 months).

A descriptive analysis of the month-3 biopsies will be conducted.

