## **Endpoints**

### **Primary endpoint**

The primary efficacy variable is the result of the Month 12 biopsy, in which success is defined by absence of detectable Gleason grade 4 or 5 prostate cancer.

The primary endpoint will be analysed as a dichotomous outcome, i.e., success (absence of any histology result positive for Gleason 4 or 5 prostate cancer at 12 months) or failure (presence of at least one result positive for Gleason grade 4 or 5 prostate cancer at 12 months).

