##### ***Efficacy population***

The efficacy population will include patients who complied with the protocol for inclusion criteria and exclusion and follow-up received the appropriate dose of TOOKAD® Soluble, LDI and energy delivered and underwent the VTP procedure, receiving the ascribed dose of TOOKAD® Soluble and light, had no major protocol deviations and provided data at the 12 month biopsy. A "major" protocol deviation is defined as one which, in the opinion of the PI, could importantly influence the result of the 12 months biopsy and which is adjudicated before the 12-month biopsy.

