### **Primary efficacy analysis**

The proportion of patients with no pattern 4 or 5 found in the 12 month biopsy will be reported along with a one-sided 90% confidence interval. Patients who have pattern 4 or 5 found before 12 months and who receive radical therapy will be treated as treatment failures. The treatment will be considered a success if the lower bound, rounded to 0.01, is 70% or higher. For a sample size of 44, this means that treatment will be declared a success if 35 or more patients respond.

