### **Secondary efficacy analysis**

#### **Biopsy results**

Biopsy results at each follow-up (3, 12, 24, 36, 48 and 60) for each definition of positive biopsy will be given as cumulative frequency, along with 95% C.I., with radical therapy as a competing risk. The alternative definitions of positive biopsy are:

1. Presence of any pattern 4 or 5 disease (primary endpoint)
2. Presence of cancer of any grade
3. Presence of any pattern 4 or 5 disease in the treated lobe
4. Presence of cancer of any grade in the treated lobe

Analyses will be repeated with radical treatment counted as an event. As retreatment at 3 months is allowed, 3 month results will be treated as a binary endpoint with 95% C.I. presented in a table.

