#### **Safety analysis**

All safety analyses will be based on the safety population. A secondary analysis will include only those patients receiving retreatment at 3 months. Results will be tabulated.

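### The SAP sentence that sets the efficacy analyses reads as leaving men retreated after month 3 out of the primary analysis, while the rest of the plan points to keeping them in

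*SAP*

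**What the plan says.** The SAP, under Efficacy analysis, applies the efficacy population to all analyses "as described above with a secondary analysis including patients undergoing retreatment at 3 months".

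Other places bear on whether retreated men belong in the primary analysis:

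- **SAP, Efficacy population.** Members must meet the entry and follow-up requirements, receive the intended drug and light, and have "had no major protocol deviations and provided data at the 12 month biopsy". Retreatment is not mentioned.
- **Protocol 6.4.10.** "A single re-treatment of lobes found positive for cancer at 3-months follow-up is allowed". The visit schedule does not change for a retreated man. The Synopsis (Methodology) allows the retreatment after any cancer at month 3.
- **Protocol 10.3.** "The primary efficacy variable is the result of the Month 12 biopsy". The SAP's Primary endpoint section defines success and failure in the same way.
- **SAP, Primary efficacy analysis.** The one override for early disease is "Patients who have pattern 4 or 5 found before 12 months and who receive radical therapy will be treated as treatment failures".
- **SAP, Biopsy results.** "As retreatment at 3 months is allowed, 3 month results will be treated as a binary endpoint".
- **SAP, Safety analysis.** "A secondary analysis will include only those patients receiving retreatment at 3 months".
- **Protocol 10.4.1 and SAP, Secondary endpoints.** These state when a retreated man counts as a responder. The primary endpoint text has no such sentence.

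**The concern.** If retreated men were already in the main analysis, a secondary analysis that includes them would add nothing. The sentence therefore suggests that they are left out first and added back second. The Safety section reinforces this: where the SAP means a retreated subgroup it writes *only*, and the efficacy sentence lacks that word. It may still be a loose version of the same subgroup statement.

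The sentence bears on the denominator of a single-arm, open-label trial with a yes/no success rule. A man is retreated because his month-3 biopsy was positive, so removing retreated men would select the primary set on a result observed after treatment. While two readings remain open, the choice between them could be made with the results in view.

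**Working it through.** **1. Passages side by side.** A retreated man who met the entry criteria, received the intended treatment, had no major deviation and has a Month 12 biopsy satisfies every written condition of the efficacy population. Retreatment is permitted, so it is not in itself a deviation. Separating the month-3 result because retreatment is allowed makes most sense if retreated men stay in afterwards. All of this points to inclusion, but by silence or inference. Only the efficacy-analysis sentence points to exclusion.

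**2. The plan's own rule.** Inputs from the SAP: one-sided 90% lower bound, rounded to 0.01, at least 0.70; 35 or more of 44 needed; assumed true rate 83.6%. The SAP does not name the interval method. The one-sided Clopper-Pearson bound, L = the 10th percentile of Beta(x, n − x + 1), reproduces the rule:

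- 35/44: L = 0.696, which rounds to 0.70: success.
- 34/44: L = 0.672, which rounds to 0.67: no success.

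**3. Can the two readings disagree?** The documents give no retreatment rate and no response rate after retreatment, so these splits are assumed. Take 44 evaluable men, 6 retreated, leaving 44 − 6 = 38.

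| Not retreated | Bound if retreated men are excluded | Retreated and clear | All 44 | Bound if included |
|---|---|---|---|---|
| 31/38 | 0.710, success | 3 of 6 | 34/44 | 0.672, no success |
| 30/38 | 0.681, no success | 5 of 6 | 35/44 | 0.696, success |

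In the first row the readings agree once 4 or more of the 6 are clear (31 + 4 = 35). In the second they agree if 4 or fewer are clear (30 + 4 = 34).

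**4. How often would they disagree?** Let A ~ Bin(38, p) count successes among men not retreated and B ~ Bin(6, q) among retreated men. Exclusion succeeds if A ≥ 31; inclusion succeeds if A + B ≥ 35. With p = q = 0.836:

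- Exclusion alone succeeds: P(A ≥ 31 and A + B ≤ 34) = 0.011.
- Inclusion alone succeeds: P(A ≤ 30 and A + B ≥ 35) = 0.115.

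With p = 0.836 and q assumed to be 0.50, the same two probabilities are 0.182 and 0.014.

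**5. Power at 83.6%,** as P(X ≥ k) for X ~ Bin(n, 0.836), with k the smallest count that meets the rule:

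- n = 44, k = 35: 0.826
- n = 40, k = 32: 0.801
- n = 38, k = 31: 0.722

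The fall is uneven because counts are discrete. Step 4 agrees with these figures: 0.722 − 0.011 + 0.115 = 0.826.

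**The case against.** The strongest reply is that the plan already answers the question. The sentence points back to a population defined without a retreatment exclusion, the endpoint is the Month 12 biopsy, and the one early-failure rule requires radical therapy. Exclusion rests on a single word. The responder rule for retreated men in the secondary endpoints also suggests that they belong to the common efficacy population. Most of this stands: the documents favour inclusion. It does not close the point. The secondary-endpoint rule could be served by the secondary analysis that includes these men, and no passage states the rule for the primary endpoint.

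It is also fair that the verdict changes only near the threshold and that the examples in the table were chosen to show it.

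A reader might infer more than the documents support:

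- **That exclusion is intended, or would flatter the result.** Retreatment may follow any cancer at month 3, including Gleason 3+3 or contralateral disease. Men with same-side deterioration are to be withdrawn, subject to an IRB exception stated in the Synopsis (Treatment conditions). Nothing shows that retreated men do worse at month 12. At a common 83.6%, exclusion mostly costs power; it favours success only if a clearly lower response after retreatment is assumed.
- **That the set falls below 44 once 7 of 50 men are retreated or lost.** Protocol 5.5.6 allows replacement of men who leave before the month-3 biopsy, and the SAP's missing-data section counts a missing Month 12 biopsy as a failure. Not every loss therefore shrinks the set.

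**Conclusion.** The point holds as a conflict of wording in the sentence that governs the primary analysis set. Its ordinary sense is exclusion; the surrounding text favours inclusion without saying so for the primary endpoint. The choice can reverse the trial's conclusion in either direction. With 6 of 44 men retreated and a common response rate of 83.6%, the two readings disagree in about 12.6% of trials (0.011 + 0.115), mostly because the smaller set has less power.

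These sizes rest on an assumed number retreated, an assumed response after retreatment, independent outcomes and the Clopper-Pearson bound. They show what could happen and do not predict what will. The point should be settled before analysis; confidence is medium because the documents already lean one way.

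**What to change.** Reword the sentence under Efficacy analysis before the Month 12 data are analysed, for example:

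> All efficacy analyses use the efficacy population. Retreatment after a positive month-3 biopsy is not a reason for exclusion; a retreated man enters the primary analysis by his Month 12 biopsy result, subject to the radical-therapy rule in the primary efficacy analysis and to the same missing-biopsy rule as any other man. A secondary analysis will report results for retreated men.

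The last sentence adopts the subgroup reading, and the authors should confirm it. If they intended exclusion, the Efficacy population section should say so and give the reason, also before that analysis.

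One related matter needs its own correction: the efficacy population requires Month 12 data, whereas the missing-data section counts a missing Month 12 biopsy as a failure. The wording above refers to that rule but does not settle it.

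The cost is a short rewording of one passage. No new data are needed, and no analysis beyond the secondary one already planned. The primary rate may move in either direction.

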### **Primary efficacy analysis**

The proportion of patients with no pattern 4 or 5 found in the 12 month biopsy will be reported along with a one-sided 90% confidence interval. Patients who have pattern 4 or 5 found before 12 months and who receive radical therapy will be treated as treatment failures. The treatment will be considered a success if the lower bound, rounded to 0.01, is 70% or higher. For a sample size of 44, this means that treatment will be declared a success if 35 or more patients respond.

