6.4.11 Post-procedure or follow-up assessments

Based on the results of post-procedure or follow-up assessments, or upon decision by them or their clinician, patients may at any time decide to undergo additional radical therapy.

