10.2.2.5 Drop-outs and censored patients

All subjects who withdraw from the trial before the VTP procedure will be considered as drop-outs. Every effort will be made to minimize dropouts.

Eligible subjects who undergo additional radical therapy (surgery or radiation) after the VTP procedure or receive medical therapies (hormone or chemotherapies) will be kept in the intention to treat population but will be excluded from the per protocol population.

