#### **Initiation of additional therapy**

Additional prostate cancer treatment is defined as any treatment for prostate cancer other than TOOKAD® Soluble-VTP, including surgery, radiotherapy (external beam, brachytherapy, focused), high intensity focused ultrasound, cryotherapy, hormonal therapy for cancer, chemotherapy for cancer.

The time to initiation of therapy will be analyzed using Kaplan-Meier estimates, presented as a survival curve with corresponding 95% confidence intervals. Subjects who did not initiate any therapy will be censored at the time of study termination. The corresponding Kaplan-Meier curve will also be presented. As a sensitivity analysis, this analysis will be repeated excluding ablative therapies and hormonal therapy, that is, an analysis of time to radical therapy (surgery, radiotherapy). Tables and figures will be provided as appropriate.

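### The SAP's early-failure rule covers radical therapy only, so a man with pattern 4/5 at Month 3 who then has cryotherapy, focused ultrasound, hormones or chemotherapy can be scored as a VTP responder

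*SAP*

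**What the plan says.** The SAP reaches failure in the primary analysis by three routes.

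- **Positive Month 12 biopsy** (Primary endpoint): "failure (presence of at least one result positive for Gleason grade 4 or 5 prostate cancer at 12 months".
- **Missing Month 12 biopsy** (end of the missing-data section, under IPSS questionnaire): "A subject with missing Month 12 biopsy will be counted as failure for the primary analysis".
- **Early failure** (Primary efficacy analysis): "Patients who have pattern 4 or 5 found before 12 months and who receive radical therapy will be treated as treatment failures".

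The third route needs two things together: pattern 4/5 and radical therapy. Under Initiation of additional therapy, the SAP shows what it means by radical: "this analysis will be repeated excluding ablative therapies and hormonal therapy, that is, an analysis of time to radical therapy (surgery, radiotherapy". The same section has a wider class: "Additional prostate cancer treatment is defined as any treatment for prostate cancer other than TOOKAD® Soluble-VTP". That class names focused ultrasound, cryotherapy, hormonal therapy and chemotherapy, but the primary analysis does not use it.

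The Efficacy population is limited to men who followed the protocol and who "had no major protocol deviations and provided data at the 12 month biopsy".

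Protocol 10.2.2.5 treats later therapy differently. Men given surgery, radiation, hormones or chemotherapy after VTP "will be kept in the intention to treat population but will be excluded from the per protocol population". It does not name cryotherapy or focused ultrasound. The SAP's Efficacy population repeats the per-protocol criteria of Protocol 10.2.2.4 without this exclusion. Protocol 6.4.11 adds that "patients may at any time decide to undergo additional radical therapy".

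**The concern.** The early-failure sentence appears to recognise that a second treatment can produce a clear biopsy that VTP did not. It then covers only part of the treatments that could do so. Ablative and systemic treatments given between the Month 3 and Month 12 biopsies fall outside it, although the SAP lists them elsewhere as cancer treatment.

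The path is plausible on the documents. Men who deteriorate at Month 3 leave for standard care (Protocol 4.1 and 5.5.4), and Protocol 2.1 describes partial-gland ablation as standard at U.S. centres.

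Where another treatment changes the Month 12 result from positive to clear, the error can only raise the VTP response rate. The trial has one arm and a fixed cut-off, so nothing offsets it.

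**Working it through.** **Step 1. How each man is scored.**

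| Course before Month 12 | Month 12 biopsy | SAP as written | Protocol 10.2.2.5 |
|---|---|---|---|
| Pattern 4/5 found, then surgery or radiotherapy | clear or none | failure by the early rule; if no biopsy, outside the Efficacy population | out of per-protocol set |
| Pattern 4/5 found, then cryotherapy or focused ultrasound | clear | responder if he stays in the Efficacy population | not named |
| Pattern 4/5 found, then hormones or chemotherapy | clear | responder if he stays in the Efficacy population | out of per-protocol set |
| No pattern 4/5 found, then radiotherapy | clear | not settled: responder or excluded | out of per-protocol set |
| Withdrawn at Month 3 | none | failure (missing-data rule) or outside the Efficacy population | depends on later therapy |

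Rows two and three are the gap.

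**Step 2. Reproduce the SAP's design.** Inputs from SAP Planned sample size: null rate p0 = 0.70, true rate p1 = 0.836, one-sided alpha 0.10, power 0.80.

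N = [(z(0.90)·√(p0(1−p0)) + z(0.80)·√(p1(1−p1))) / (p1−p0)]²
= [(1.2816 × 0.4583 + 0.8416 × 0.3703) / 0.136]² = 43.7, rounded up to 44. This matches the SAP.

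The cut-off comes from SAP Primary efficacy analysis: the one-sided 90% lower bound, rounded to 0.01, must reach 0.70. The exact (Clopper-Pearson) bound is the 10% quantile of Beta(r, 44−r+1).

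| Responders of 44 | Lower bound | Rounded | Result |
|---|---|---|---|
| 35 | 0.6964 | 0.70 | success |
| 34 | 0.6716 | 0.67 | fail |
| 33 | 0.6472 | 0.65 | fail |

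The SAP's figure of 35 is reproduced. Its exact operating characteristics are alpha 10.9% and power 82.6%. The SAP does not name the interval method, but the cut-off is also 35 with Wald, Wilson and Jeffreys bounds (at 34 they give 0.692, 0.683 and 0.684).

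**Step 3. Effect of misclassified men.** The documents give no rate of non-radical treatment before Month 12, so the count m is an assumption. It refers to men who would have had pattern 4/5 at Month 12 without the other treatment. Each adds 1/44 = 2.3 percentage points.

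Model A: exactly m true failures are scored as responders, so 35−m true responders are enough. The false-success chance is P(X ≥ 35−m) with X ~ Binomial(44, 0.70).

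Model B: m is the expected number, so the scored rate is 0.70 + m/44 and the chance is P(X ≥ 35) at that rate.

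| m | Model A | Model B |
|---|---|---|
| 0 | 10.9% | 10.9% |
| 1 | 18.9% | 18.3% |
| 2 | 29.4% | 28.5% |
| 3 | not computed | 41.3% |
| 4 | not computed | 55.8% |

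**Step 4. At the boundary.** If 35 of 44 are scored as responders and one belongs to the gap, correct scoring gives 34 of 44. The bound falls from 0.696 to 0.672 and the conclusion changes from success to failure.

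**The case against.** Four points on the other side deserve weight.

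1. **Failure has other routes.** A reader might infer from the early-failure sentence that a man fails only if he has both pattern 4/5 and radical therapy. The documents do not support that. A positive Month 12 biopsy is failure whatever therapy was given, and a missing one is failure under the missing-data rule. The gap concerns only men with a clear Month 12 biopsy.

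2. **Some of these men may never be counted.** A reader might also infer that irradiated or hormone-treated men with clear biopsies are certain successes. Protocol 10.2.2.5 would remove them from the per-protocol set, and the Efficacy population clauses on follow-up and on major deviations judged by the PI might do so too. Their scoring is ambiguous. This does not close the gap. The SAP does not carry over the exclusion, cryotherapy and focused ultrasound are not named in it, and further therapy is hard to call a deviation when the Protocol permits radical therapy at any time.

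3. **The path is narrow.** After a positive Month 3 biopsy the Protocol provides for VTP re-treatment or, in defined cases, withdrawal. A withdrawn man may have no Month 12 biopsy, and then he is not a success. This limits the number of men affected. It also exposes a conflict: the missing-data rule counts him as a failure, while the Efficacy population leaves him out.

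4. **A clear biopsy might have occurred anyway.** A man whose Month 12 biopsy would have been clear without the other treatment adds no bias. This stands, and it is why the figures are conditional. It also means that failing every man who has any other treatment, including one with no pattern 4/5 found, would create a composite endpoint that can be debated.

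The SAP does report time to additional treatment, and it repeats its secondary biopsy analyses with radical treatment counted as an event. Some cases would therefore be visible, but neither analysis corrects the primary result.

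**Conclusion.** The concern holds in a limited form. The primary analysis has no rule for non-radical cancer treatment given after pattern 4/5 has been found and before Month 12. Under the stated rules, such a man with a clear Month 12 biopsy who stays in the Efficacy population is a VTP responder. The reading is firmest for cryotherapy and focused ultrasound. For hormones and chemotherapy it depends on whether the Protocol's per-protocol exclusion is meant to apply.

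The size is conditional. With a true rate of 70%, N=44 and a cut-off of 35, one or two men who would otherwise have failed raise the chance of false success from 10.9% to about 19% or 29%. One is enough to reverse a result of exactly 35 of 44. It would be wrong to infer that the trial's error rate is 19% or 29%, because the documents give no sign of how many such men to expect. If there are none, the result is unaffected.

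**What to change.** 1. In SAP Primary efficacy analysis, widen the early-failure rule, for example: *A man in whom pattern 4 or 5 is found before 12 months, and who receives any additional prostate cancer treatment (as defined under Initiation of additional therapy) before his Month 12 biopsy or, if he has none, before the Month 12 visit, is a failure and stays in the primary denominator.* VTP re-treatment allowed by the Protocol is unaffected, because the SAP's definition leaves VTP out.
2. Add a sensitivity analysis that counts any additional prostate cancer treatment before Month 12 as failure, whether or not pattern 4/5 was found.
3. Reconcile the SAP's Efficacy population, its missing-biopsy rule and Protocol 10.2.2.5 with this rule, so that each man is scored in one way.

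The cost is one sentence in the primary analysis, one extra sensitivity analysis and matching edits to the passages in item 3, settled before the primary analysis is run. N=44 and the 35-of-44 cut-off stay as they are. The reported response rate may be slightly lower.

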This study is a phase IIb trial using optimal dose of TOOKAD® Soluble and optimal light-energy level conditions that were determined in previous phase I and II studies and confirmed by the phase III studies among patients with localized prostate cancer. Partial gland ablation therapy using thermal approaches, as an alternative to radical treatments for low-volume prostate cancer, is a treatment option currently being offered to men with prostate cancer in the U.S. as a tailored means to manage their disease with fewer side effects. Previous studies of TOOKAD® Soluble treatment have suggested that this non-thermal approach is an effective therapeutic strategy to achieve ablation of the prostatic tissue that contains the cancer lesion in this patient population. Considering the available clinical data, a phase IIb is considered appropriate at this stage, with the main aim of confirming, in intermediate risk patients, previous findings in low and favorable intermediate risk prostate cancer patients. Moreover, a single center design was also considered appropriate, as it allows for optimal standardization of the technique and better control over data acquisition.

NUMBER OF PATIENTS:

In order to obtain at least 44 evaluable patients, a total of 50 patients will be included and will be treated with TOOKAD® Soluble VTP in this study.

DRUG DESCRIPTION AND PREPARATION:

TOOKAD® Soluble - padeliporfin di-potassium (WST11) Drug Product is a dark coloured powder for solution for injection. It is packaged in amber glass vials. It is manufactured in two different presentations:

- 200 mg TOOKAD® Soluble in a 30 mL vial with blue flip-off cap, to be reconstituted, just before administration, with 20 mL of 5% dextrose solution for injection
- 400 mg TOOKAD® Soluble in a 50 mL vial with white flip-off cap, to be reconstituted, just before administration, with 40 mL of 5% dextrose solution for injection

The two presentations have the same formulation which is produced in exactly the same process and they differ only in the amount of TOOKAD® Soluble per vial, the size of the vial and the colour of the flip-off cap.

For both presentations the final concentration of TOOKAD® Soluble solution to be injected is 10 mg/mL.

INCLUSION CRITERIA:

Subjects will be eligible for inclusion in the study if all of the following criteria are met:

1. Men over 18 years of age.

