10 STATISTICS

10.1 Sample size

The trial sample size was calculated to achieve 80% power to reject the null hypothesis $H_0 = "r \leq 70\%"$, using a one-sided exact binomial test with 5% alpha risk.

From historical clinical data, the true response rate is expected to be greater than 90%. However, to remain conservative the true response rate could only be estimated from localized intermediate-risk prostate cancer patients patients who underwent the TOOKAD Soluble procedure and for whom biopsies were available after 12 months. Using these conservative estimates we identified a true response rate is greater than 83.6% with >80% posterior probability (assuming a beta-binomial model).

Using this conservative choice for true response rate $r=83.6\%$ a minimum of $N=44$ patients with fully evaluable data is required.

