#### **Planned sample size**

For an assumed true response rate of 83.6%, we can discount a response rate of 70% at a one-sided alpha of 10%, with a power of 80% if we have a sample size of 44 patients.

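### The SAP's success rule of 35 of 44 does not run at the stated one-sided 10%, and with no interval method named the pass mark at 46, 47 and 50 patients is open by one responder

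*SAP*

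**What the plan says.** The SAP's Planned sample size section assumes a true response rate of 83.6% and says that 70% can be ruled out "at a one-sided alpha of 10%, with a power of 80% if we have a sample size of 44 patients".

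Its Primary efficacy analysis section says that the response proportion "will be reported along with a one-sided 90% confidence interval". The decision rule follows: "The treatment will be considered a success if the lower bound, rounded to 0.01, is 70% or higher". One worked case is given: "For a sample size of 44, this means that treatment will be declared a success if 35 or more patients respond". No interval method is named there, and the general statement on methods names only the software (Stata or R).

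The protocol's section 10.1 bases the sample size on a test of 70% "using a one-sided exact binomial test with 5% alpha risk". Section 10.3, on the analysis of the primary endpoint, names no test. The protocol synopsis explains the recruitment target: "In order to obtain at least 44 evaluable patients, a total of 50 patients will be included".

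**The concern.** This is the only formal success test in a single-arm, open-label trial, so its error rate should be the one that the plan states. Two features put that in doubt.

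First, a one-sided 90% exact lower bound of at least 70% would guarantee a type I error of at most 10%. Rounding the bound to two decimals lets any value from 0.695 upwards pass, and the guarantee is lost.

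Second, the number analysed will probably not be exactly 44. At other sizes a reader must apply the rule himself, and different standard intervals for a proportion can then give different pass marks. If the method is settled only when the count is known, one responder could separate success from failure.

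**Working it through.** **Inputs.** Null rate 0.70, true rate 0.836, one-sided level 0.10 and n = 44 (SAP, Planned sample size). Rule: lower bound rounded to 0.01 at least 0.70, mark 35 of 44 (SAP, Primary efficacy analysis). Planned range 44 to 50 (protocol synopsis).

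**Formulas.** For pass mark c, size = P(X ≥ c | n, 0.70) and power = P(X ≥ c | n, 0.836), with X binomial. The Clopper-Pearson bound L for x responders solves P(X ≥ x | n, L) = 0.10. The Wilson bound, with p = x/n and z = 1.2816, is [p + z²/2n − z√(p(1−p)/n + z²/4n²)] / (1 + z²/n).

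**1. The plan's own figures.** The usual normal approximation gives n = [(1.2816 × √0.21 + 0.8416 × √(0.836 × 0.164)) / 0.136]² = 43.7, so 44 reproduces. At 35/44 the bounds are Clopper-Pearson 0.6964 (0.70 after rounding), Agresti-Coull 0.7069, mid-P 0.7075, Wilson 0.7076, Jeffreys 0.7089 and Wald 0.7175. At 34/44 the highest is Wald at 0.6918, which fails. The mark of 35 is therefore right under all six methods, and for that reason it does not show which one was meant.

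**2. Exact properties at 44.**

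| Pass mark | Size at 70% | Power at 83.6% |
|---|---|---|
| 34 | 18.9% | 90.5% |
| 35 (SAP) | 10.9% | 82.6% |
| 36 | 5.6% | 71.1% |

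No row has size at or below 10% together with power of at least 80%. The smallest n that allows both is 45, with 36 responders (9.3%, 80.7%).

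**3. Other sizes in the planned range, rounded rule.** The last column refers to Wilson, Jeffreys, Agresti-Coull, mid-P and Wald.

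| n | Clopper-Pearson: mark (size, power) | The other five |
|---|---|---|
| 44 | 35 (10.9%, 82.6%) | same |
| 45 | 36 (9.3%, 80.7%) | same, except Wald 35 (16.5%) |
| 46 | 37 (7.9%, 78.7%) | all 36 (14.3%, 87.8%) |
| 47 | 38 (6.7%, 76.7%) | all 37 (12.4%, 86.3%) |
| 48 | 38 (10.7%, 84.7%) | same |
| 49 | 39 (9.2%, 83.1%) | same, except Wald 38 (15.9%) |
| 50 | 40 (7.9%, 81.3%) | all 39 (13.9%, 89.3%) |

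Example at 39/50: Clopper-Pearson is 0.6869, which rounds to 0.69 and fails. Wilson is (0.78 + 0.0164 − 0.0769) / 1.0328 = 0.6967, which rounds to 0.70 and passes. The other four lie between 0.6962 and 0.7049 and pass.

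The difference in size between the two marks is 6.4 points at 46, 5.7 at 47 and 6.0 at 50.

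**4. Effect of the rounding.** With Clopper-Pearson and no rounding, the marks in this range change only at 44 (36: 5.6%, 71.1%) and 48 (39: 5.7%, 74.6%). Size is then at or below 10% at every n, and power reaches 80% only at 45, 49 and 50.

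**The case against.** The best defence is that the documents already point to one method. Protocol 10.1 names an exact binomial test, and of the six bounds above only Clopper-Pearson needs the rounding to accept 35 of 44. That inference is reasonable and it narrows the point: one clarifying word would close most of the gap. It remains an inference. The protocol's reference concerns the sample size and a 5% level, and the SAP does not carry it over.

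It is also fair to say that the five alternatives are a selection. Continuity-corrected Wilson gives the Clopper-Pearson mark at every size from 44 to 50. A reader might infer from the table that the exact bound is a lone outlier, or that the result can be switched at will; neither is supported. The gap is one responder, at three of the seven planned sizes, or five if Wald is admitted.

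A reader might also infer that 35 of 44 is a miscalculation. It is not: it follows from the SAP's rule under all six methods. What is wrong is the 10% level attached to it.

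Finally, the SAP both restricts the efficacy population to patients who "had no major protocol deviations and provided data at the 12 month biopsy" and states that "A subject with missing Month 12 biopsy will be counted as failure for the primary analysis". With 6 of 50 biopsies missing, 35 responders could be read as 35/44 or 35/50. That contrast is large, but it measures the conflict over the denominator and not the choice of interval, so it adds nothing to the size of this point.

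**Conclusion.** The point stands in two parts. The stated operating characteristics at 44 are not those of the stated rule: exact size is 10.9% against 10%, and no cutoff at 44 gives both 10% and 80%. The excess of 0.9 points is small and calls for restatement, not redesign. In addition, the rule is incomplete for an analysed number other than 44. At 46, 47 and 50 the unnamed method is worth one responder and 5.7 to 6.4 points of type I error.

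This rests on reading the rounding on the proportion scale (0.695 becomes 0.70), on the SAP's 10% level and 83.6% alternative, and on an analysed number between 44 and 50. The level (5% in the protocol's synopsis and section 10.1, 10% in the SAP) and the denominator are separate conflicts. Both must be settled before any table of pass marks is final.

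**What to change.** In the SAP's Primary efficacy analysis, before the Month 12 analysis, name the Clopper-Pearson one-sided lower bound and give pass mark, exact size and power for each n from 44 to 50. Then choose one of two forms.

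- **Keep the rounding.** Use the Clopper-Pearson column of the table above, and restate the level in Planned sample size as 10.9% at 44.
- **Drop the rounding.** Size then stays at or below 10%. The marks become 36 at 44 and 39 at 48, the rest of the column is unchanged, and 80% power should no longer be claimed at 44.

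If the level is reconciled to 5%, the Clopper-Pearson mark at 44 is 36 with rounding (bound 0.6958; 5.6%, 71.1%) or 37 without (2.6%, 56.4%). At 50 it is 41 either way (4.0%, 70.1%).

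The cost is one sentence and a small table. Keeping the rounding means reporting a slightly less favourable level. Dropping it lowers power from 82.6% to 71.1% at 44 and from 84.7% to 74.6% at 48. In either form, naming Clopper-Pearson rather than Wilson under the SAP's rounded rule gives up power at 46 (78.7% v 87.8%), 47 (76.7% v 86.3%) and 50 (81.3% v 89.3%).
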